### 6.2 Describe:

- There are no known risks to medical ultrasound imaging.
- CEUS Lumason® (sulfur hexafluoride lipid type-A microspheres) will be obtained through IDS pharmacy and administered through an already existing IV catheter by an RN or a radiology technologist trained and certified to administer the Lumason® contrast agent, and an abdominal ultrasound will be completed.
- Lumason (sulfur hexafluoride lipid-type A microspheres) is the investigational product. The recommended dose of Lumason for children is 0.03 mL/kg up to a maximum dose of 2.4mL injected into a peripheral intravenous catheter. See individualization of dose below.
  - 1. Follow the Lumason injection with a flush of 5 ml of 0.9% Sodium Chloride Injection, USP.
  - 2. The maximum total dose for children as listed in the package insert should not exceed 2.4 mL in any 10-minute period. With a maximal total dose of 4.8 mL in any one patient during a single exam.

- 6.3 Protected health information (PHI) to be collected for the purpose of this study alone will include; MRN, date of transplant, dates of ultrasound exams (attached data collection sheet). This information will be documented in RedCap. Within RedCap, there will be two separate files. One file will include minimal PHI (dates of service) and contain study data according to an assigned study ID number. The second file, will contain a master list of subjects linking the subject PHI with the assigned study ID number. The research record generated will consist of an excel spreadsheet from the data dictionary within RedCap. Security measures include: storage of the data on a password protected computer in a restricted assess departmental folder limited to only study personnel.
- 6.4 Participants in this study have two options regarding data collection, they may consent to take part in the CIBMTR Research Database or they may take part in only this study.

Data Collection Procedures for those that consent to take part in the CIBMTR Research Database:

Subjects may have already consented to take part in the CIBMTR Research Database (IRB# 11120281). If they are not yet taking part in that study, they will be given the option to consent for CIBMTR Research Database at the time they are consenting for this study.

If a subject chooses to take part in the CIBMTR database, data entered as part of this protocol will be entered into the CIBMTR database at the end of local site enrollment.

Data will provided to CIBMTR in the form of a spreadsheet and will be password protected and sent to CMH only for data analysis.

Clinical and outcome data, including DOB, dates of service, exams, lab values and clinical timepoints will be evaluated.

Data Collection Procedures for those that do not consent to take part in the CIBMTR Research Database:

For subjects that consent to BMT Elastography (Internal) study, but do not consent to have their data entered into the CIBMTR database will have their clinical variables entered into a local REDCap database. Those data points will include DOB, dates of service, exams, lab values and clinical timepoints

Data Collection Procedures for both groups:

Additional clinical variables (not captured in the CIBMTR database needed to define our objectives) and elastography variables will be retrospectively extracted from the patients' electronic medical records and entered into REDCap. We will collect a number of variables based on the CIBMTR +100 Day outcome form and we will collect variables related to the modified Seattle criteria,

Baltimore criteria and the new EBMT criteria. We will also collect clinical and laboratory parameters of liver disease to help us evaluate for other hepatic complications from HCT. We will use the adult and pediatric EBMT criteria to determine the date on which the patient was first diagnosed with SOS. The date of diagnosis will be the first day on which the patient meets the EBMT criteria for their cohort (adult or pediatric). We will also use clinical data to grade SOS severity, to detect other hepatic complications from HCT, and to inform our SOS predictive modeling. For SOS grading, the day on which the patient meets the severity criteria for that particular grade will be recorded.

# 7.0 Data and Specimen Banking

7.1 N/A

8.0 Genetic Analysis Information 8.1 N/A

# 9.0 Sharing of Results with Subjects

- 9.1 US SWE results will be blinded from clinicians and patients.
- 9.2 Any unexpected findings will be communicated to the ordering physician by [name] via phone or email.

# **10.0 Study Timelines**

10.1 Describe:

- An individual's participation in the study will be during their inpatient stay for their BMT. Once the patient is discharged or Day +100 after BMT is reached, whichever comes first, subject will no longer be in the study.
- July 1, 2018 through June 30, 2020
- June 30, 2021

# 11.0 Inclusion and Exclusion Criteria

11.1 Describe the criteria that define who will be included or excluded in your final study sample.

Inclusion Criteria

- Subject's age 1 month through 21 years whom are undergoing myeloblative conditioning regimen prior to BMT are eligible for the study.
- Subjects will be identified by treating BMT physician
- 1 month through 21 years

• July 1, 2018 through June 30, 2020

### Exclusion Criteria

- Any other medical or social condition that in the opinion of the investigator would make them unsuitable to participate.
- Indicate specifically whether you will include or exclude each of the following special populations: (You may not include members of the following populations as subjects in your research unless you indicate this in your inclusion criteria.)
  - Adults unable to consent: Include
  - Individuals who are not yet adults: Include
  - Pregnant women: Exclude
  - Prisoners: Exclude
  - Wards of the state: Exclude

### **12.0** Vulnerable Populations

- 12.1 If the research involves individuals who are vulnerable to coercion or undue influence, describe additional safeguards included to protect their rights and welfare.
  - All subjects and family will be given sufficient time to review and determine if they would like to participate in the study.
  - Subjects over the age of 7 will be required to provide assent for study procedures. Subject enrollment is completely voluntary.

# **13.0** Local Number of Subjects

13.1 We anticipate enrolling 80 subjects.

# 14.0 Screening and Recruitment Methods

- *14.1* Candidates for the study will be identified by BMT physician and approached for consent prior to start of conditioning regimen.
- 14.2 BMT patients are the source of subjects
- 14.3 Subjects will be identified and referred by BMT provider
- 14.4 A Waiver of HIPAA Authorization for Recruitment purposes only is requested to ensure subjects meet eligibility criteria for enrollment. Pre-screening information will not be recorded.
- 14.5 Subjects will be informed of the study by their treating BMT physician and then approached by a member of the study team for consent.

# 15.0 Reimbursement, Payment and Tangible Property provided to subjects

15.1 N/A

# 16.0 Withdrawal of Subjects

- *16.1* Subjects may be withdrawn at the discretion of their treating physician or at the LAR/subject request at any time during their inpatient stay. All data collected prior to the date of withdrawal will be kept for analysis.
- 16.2 Notification of request of withdrawal to study team is required
- 16.3 This is a minimal risk study, thus no follow-up is needed.

### **17.0** Risks to Subjects

17.1 We do not anticipate any additional risks to this study as all patients will already have IV access per SOC for BMT and no additional line placements will be required as part of this study. All subjects will be monitored during the Lumason CEUS examination by radiology personnel and by BMT staff after the exam for any adverse events.

Reported risks related to Lumason administration include:

Serious cardiopulmonary reactions, including fatalities, have occurred uncommonly in adults during or shortly following administration of ultrasound contrast agents, including Lumason. These reactions typically occurred within 30 minutes of administration. Hypersensitivity reactions such as skin erythema, rash, urticaria, flushing, throat tightness, dyspnea, or anaphylactic shock have uncommonly been observed following the injection of Lumason. The exclusion criteria eliminate any subjects with a known cardiac abnormality or a known sensitivity to sulfur hexafluoride, so we do not anticipate that these reactions will occur. Resuscitation personnel and equipment will be available during the study treatment and follow-up period.

Adverse Reaction	Number	(%)
Any Adverse Reaction	340	5
Headache	65	1
Nausea	37	0.5
Dysgeusia	29	0.4
Injection site pain	23	0.3
Feeling hot	18	0.3
Chest discomfort	17	0.2
Chest pain	12	0.2
Dizziness	11	0.2
Injection site warmth	11	0.2

17.2 This study poses a minor increase over minimal risk as it does not hold the prospect of direct benefit for the individual subject, but the

intervention presents an experience that is reasonably commensurate with those inherent to the subject's medical situation and is likely to yield generalizable knowledge about the disorder which is of vital importance to the detection of VOD/SOS. Physicians will be blinded to the results of the imaging.

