### Ultrasound Examinations and Timeline

After enrollment and within two weeks prior to starting their conditioning regimen, a limited abdominal US with Doppler measurements of the hepatic arteries, hepatic and portal veins, contrast enhanced ultrasound (CEUS) of the liver, as well as SWE will be performed.

Subjects will be undergo US examinations based on disease course as outlined below:

- 1. All Patients: Patients will undergo limited abdominal US with Doppler, CEUS and SWE once a week upon admission for conditioning until the patient day +30 BMT or discharge, whichever comes first.
- 2. Inpatient SOS: patients will undergo limited abdominal US with Doppler, CEUS and SWE once a week upon admission for conditioning until resolution of SOS.
- 3. Late Onset SOS: patients will undergo limited abdominal US with Doppler, CEUS and SWE once a week upon admission for conditioning until resolution of SOS.

The clinical team will order US, CEUS and SWE exams when patients have clinical suspicion for SOS and we will include these exams in our analysis. All imaging will be performed using GE Logiq E9 US machines by dedicated pediatric sonographers and interpreted by board-certified pediatric radiologists. Twelve shear wave velocity measurements will be taken 2-3 cm below the liver capsule at the mid-clavicular line in the right hepatic lobe and another 12 will be taken in the left hepatic lobe near midline

avoiding areas of vasculature (24). By necessity, the sonographer and interpreting radiologist will not be blinded to the clinical status of the patient. US and clinical data will be collected weekly and managed using REDCap electronic data capture tools hosted at Children's Mercy Hospital (25).

	ALL PATIENTS		INPATIENT SOS	LATE ONSET SOS
	Prior to	Start of Conditioning	Through	Through Resolution of
	Conditioning	through Day +30	Resolution of SOS	SOS
	Screening	Once per Week	Once per Week	Once per Week
Limited Abdomen and Limited Abdominal Doppler Ultrasound	X	Х	Х	X
Contrast Enhanced Ultrasound	X	X	X	X
Ultrasound Elastography	X	X	X	X

Table 3. Ultrasound Timeline

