### **21.0** Provisions to Monitor the Data to Ensure the Safety of Subjects

21.1 Describe:

- All data collected on subjects who receive study drug will be analyzed for safety. The proportion of patients with specific adverse events will be reported as well as the worst grade observed across all adverse events. The maximum confidence interval width for these estimates is 16.8%. If the observed estimated adverse event proportion is 10%, the 95% confidence interval is (5.3, 15.6%).
- Safety information will be collected at the time of study visit when the patient is monitored during contrast administration.
- Safety data collection will begin with the first participant and participants will be monitored in real time.

- The PI or an assigned co-investigator will be responsible for monitoring the data.
- Cumulative data will be reviewed on a weekly basis beginning with the first study participant.
- All data collected on subjects who receive study drug will be analyzed for safety. The proportion of patients with specific adverse events will be reported as well as the worst grade observed across all adverse events. The maximum confidence interval width for these estimates is 16.8%. If the observed estimated adverse event proportion is 10%, the 95% confidence interval is (5.3, 15.6%).
- Any adverse event resulting from the contrast agent requiring an ICU admission will trigger an immediate suspension of the research.

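### Section 17.1 relies on exclusions for known cardiac abnormality and sulfur hexafluoride sensitivity that section 11.1 does not contain

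*Protocol*

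**What the plan says.** Section 17.1 (Risks to Subjects) describes serious cardiopulmonary reactions, some fatal, reported uncommonly in adults given ultrasound contrast agents including Lumason. It also describes uncommon hypersensitivity reactions, up to anaphylactic shock. It then says: "The exclusion criteria eliminate any subjects with a known cardiac abnormality or a known sensitivity to sulfur hexafluoride", and concludes "so we do not anticipate that these reactions will occur".

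Section 11.1 holds the eligibility rules. The main inclusion criterion is: "Subject's age 1 month through 21 years whom are undergoing myeloblative conditioning regimen prior to BMT are eligible for the study". The only medical exclusion is a general one: "Any other medical or social condition that in the opinion of the investigator would make them unsuitable to participate". The rest is a list of special populations, of which three are excluded; the first is entered as "Pregnant women: Exclude", and the other two are prisoners and wards of the state.

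Exposure is set in section 6.1. All patients have contrast-enhanced ultrasound before conditioning and then "CEUS and SWE once a week upon admission for conditioning until the patient day +30 BMT or discharge, whichever comes first". Patients with SOS continue weekly until it resolves.

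**The concern.** Section 17.1 reports what the exclusion criteria do, and section 11.1 does not bear it out. The error matters because 17.1 uses the claim as its reason for not expecting the most serious reactions to the study's contrast agent. If the exclusions are absent, that reason is absent too.

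The practical risk is that a child with a known cardiac abnormality or a known sensitivity to sulfur hexafluoride satisfies section 11.1 and receives Lumason repeatedly, with exclusion left to individual judgement. There is also a review risk. Section 19.0 asks for the risk/benefit assessment to be based on sections 17.0 and 18.0. The study is placed in Category 3 (greater than minimal risk, no prospect of direct benefit), and 18.1 states that subjects do not benefit. An ethics board relying on 17.1 would credit the study with a protection that its criteria do not provide.

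**Working it through.** There is no figure to recompute. The check sets the claim in 17.1 against every place in the protocol where it could be made good.

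**Step 1: count what 11.1 excludes.**

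| Exclusion in section 11.1 | Names a cardiac abnormality? | Names sulfur hexafluoride sensitivity? |
|---|---|---|
| Investigator-discretion item | No | No |
| Pregnant women | No | No |
| Prisoners | No | No |
| Wards of the state | No | No |

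Exclusions listed: 1 + 3 = 4. Conditions claimed in 17.1: 2. Claimed conditions found in the list: 0 of 2.

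**Step 2: look for an equivalent rule elsewhere.**

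- Inclusion criteria (11.1): age, myeloablative conditioning, identification by the treating BMT physician, and enrolment dates. No cardiac or allergy condition.
- Lumason procedure (6.2): supply, dose, flush, maximum dose and staff qualification. No check for either condition before injection.
- Screening and recruitment (14.0): identification and referral by the BMT physician. No check.
- Withdrawal (16.1): at the treating physician's discretion or on request. No mandatory trigger.
- Consent process (25.1): timing and place. No check.

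**Step 3: see whether the discretion item makes the claim true.** Section 17.1 says that any subject with either condition is eliminated. The discretion item excludes only those whom the investigator judges unsuitable, and it names no condition. Two investigators could decide differently about the same child and both would comply with 11.1. A permission of that kind does not amount to the elimination that 17.1 asserts.

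**Step 4: see whether the later safeguards fill the gap.** Section 17.1 provides monitoring during and after the examination, with resuscitation staff and equipment available. Section 21.1 adds: "Any adverse event resulting from the contrast agent requiring an ICU admission will trigger an immediate suspension of the research". These measures operate once a reaction has begun or has happened. The argument in 17.1 rests on keeping susceptible subjects from being dosed at all.

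**Step 5: consider whether missing text explains the gap.** The exclusion list shows no redaction mark or break. The pages removed from the file precede the revision history, well before section 11. Both statements are in the current body of the protocol. Contrast ultrasound was added at revision 2, which would fit section 11 not having been updated at that point. That is an inference, and the finding does not depend on it.

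**The case against.** The best reply is that the protocol should be read as a whole. Section 17.1 is also protocol text. It tells the investigator that these subjects are not meant to be in the study, and the discretion item gives the power to keep them out. Every subject is identified and referred by a treating BMT physician before any dose, that physician can withdraw a subject before a later dose, and Lumason is given by trained and certified staff through the pharmacy. The reactions are described as uncommon, and the serious cardiopulmonary ones are reported for adults. The defect touches no endpoint or analysis.

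Much of this is fair as context. The intent to exclude is visible, some gatekeeping precedes dosing, and the number of subjects affected may be small. But none of these steps requires anyone to ask about either condition or to act on the answer, so the statement that the criteria eliminate such subjects remains untrue. That the reactions are uncommon does not help either, because 17.1 bases its expectation on the exclusions.

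Two further points stand and shape the fix. The phrase about cardiac abnormality is not defined anywhere in the protocol. And excluding known sensitivity cannot rule out a reaction in a subject whose sensitivity is not yet known.

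**Conclusion.** The concern holds. Neither of the 2 exclusions asserted in section 17.1 is among the 4 listed in section 11.1, and no other section supplies them. Exclusion of these subjects is at most discretionary, and the conclusion in 17.1 that the reactions are not anticipated has no explicit support in the criteria.

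The direct effect is confined to candidates with a known cardiac abnormality or known sulfur hexafluoride sensitivity. The protocol does not give their number, so no count of subjects or injections is claimed. The conclusion assumes only that section 11.1 is the operative list of criteria and is complete as shown. An unseen statistical analysis plan would not change it, since eligibility rules belong in the protocol. The point should be fixed before further enrolment, because it misstates a participant-safety rule in a study whose subjects stand to gain no direct benefit.

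**What to change.** Add two exclusion criteria to section 11.1: known cardiac abnormality, with a definition that can be applied consistently, and known sensitivity to sulfur hexafluoride. Record a check of both, on the eligibility form, before the first contrast-enhanced ultrasound. Once they are added, 17.1 should say that the exclusions reduce the risk of these reactions, since unknown sensitivity remains possible.

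If the exclusions are not intended, delete from 17.1 both the claim and the conclusion that follows it, and make the same correction in the consent text if it repeats them.

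The cost is a short amendment and an update to the eligibility checklist. Some candidates may become ineligible. How many cannot be judged from the protocol and depends on how the cardiac term is defined, so the definition should be agreed with that in mind, given the target of 80 subjects.

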### **18.0** Potential Benefits to Subjects

18.1 There are no potential benefits to subjects for participation to this study.

# 19.0 Investigator Assessment of Risk/Benefits Ratio: (IRB makes the

**final determination)** *Based upon your response in Sections 17.0 and 18.0, please provide your assessment of risk and benefits in below table.* 

Select as applicable:	Pediatric R	isk Category:
	Category 1	Research not involving greater than minimal risk (45 CFR §46.404 and 21 CFR §50.51)
	Category 2	Research involving greater than minimal risk but presenting the prospect of direct benefit to the individual subjects. (45 CFR §46.405 and 21 CFR §50.52)
X	Category 3	Research involving greater than minimal risk and no prospect of direct benefit to individual subjects, but likely to yield generalizable knowledge about the subject's disorder or condition. (45 CFR §46.406 and 21 CFR §50.53)
	Category 4	Research not otherwise approvable which presents an opportunity to understand, prevent, or alleviate a serious problem affecting the health or welfare of children. (45 CFR §46.407 and 21 CFR §50.54)
Select if applicable:	Adult Risk Category:	
	Not Greater	than Minimal Risk
	Greater than Minimal Risk	

### **20.0** Data Management and Confidentiality

- 20.1 All identifiable data will be stored in REDCap and InteleViewer (PACS viewing system used by Department of Radiology) housed at CMH and will be password protected. Patient DOB, MRN and exam date and type are necessary to identify data points of interest. A separate master linking list with patient MRN will be kept within CMH internal server and will be destroyed upon completion of the study. All recorded dates (e.g. dates of US SWE, HCT and conditioning regimen) will be destroyed upon completion of data analysis.
- 20.2 [name] will have access to our Research PACS, which is a limited to exams performed for research purposes. These exams are manually placed into the research PACS by a member of the radiology research team. All data in the research PACS is

identifiable for purposes of this research study, but [name] will only access this information as part of this research study.

- 20.3 A certificate of confidentiality will not be sought for this study.
- *20.4* Study data will be evaluated by the PI throughout the duration of the study for QA.
- 20.5 Patient information will be maintained in a REDCap application and will be housed within the CMH Data Center by the Division of Biomedical Informatics. The hosting server has an internal failover two-node cluster. The CMH Data Center is constantly staffed by qualified personnel and physical access is limited to authorized personnel. The Center has optimized conditions for the servers and stabilized electrical supply. The database has a full backup. The database server is located inside the CMH corporate firewall. A person must have CMH system access to loin. Additional security for the study patient database restricts access to only those persons specifically granted authorization by the Principle Investigator. It is possible for data to be downloaded from REDCap. Individuals who lack authority to see confidential data can download reports with non-identifiable data only. The core research group will have the ability to download sensitive fields and if such a download occurs, REDCap maintains a record of who, what, when, and to where copies of the database were imported.
- 20.6 Consented subjects will be provided a printed calendar outlining their research ultrasound schedule at the time of admission for the duration of their enrollment in the study. Each calendar will be specific to each subject's treatment and clinical course, which is being performed as standard of care.

For subjects that are enrolled in additional research ultrasound studies, all research ultrasound exams will be listed on the same calendar.

